9.4.4 Safety Analyses

The total number of adverse events (AE) will be summarized by severity, drug-relatedness, and whether it is an SAE and then also the total number of participants experiencing an AE will be summarized by study phase and/or study arm.

9.4.5 Adherence and Retention Analyses

Adherence to treatment regimen will be determined by the percentage of treatment insufflated per the prescribed treatment amount at each evaluable study time point. Mean adherence will be determined at each study time point during the non-blinded study phase and by study arm during the blinded phase. Each subject's medication use and study diary will be reviewed at every visit to measure adherence Patients withdrawing prematurely from the study will be summarized by study timepoint and phase (blinded/non-blinded) and study arm (if applicable) and reason if available.

9.4.6 Baseline Descriptive Statistics

Descriptive summaries will be performed separately for the non-blinded study phase and by study arm for the blinded study phase using means, standard deviations, and frequencies and percentages. There will be no inferential statistics used as randomization should eliminate the potential for bias.

9.4.7 Planned Interim Analysis

Not applicable

9.4.7.1 Safety Review

Administration of the study agent will be halted when three grade 3 AEs determined to be "probably related" are reported to the PI. The PI will notify the IRB immediately when the third grade 3 event is reported and enrollment screens will stop accepting new study participants and the active participants will be contacted via phone and if necessary certified mail, to immediately discontinue the spray.

9.4.7.2 Efficacy Review

Not applicable

9.4.7.3 Additional Sub-Group Analyses

Not applicable

9.4.7.4 Multiple Comparison/Multiplicity

Not applicable

9.4.7.5 Tabulation of Individual Response Data

Not applicable

9.4.7.6 Exploratory Analyses

Changes in CGI and TFI from baseline (week 3) to week 6 during the blinded study phases will be determined and summarized using means and standard deviations for each study arm. A descriptive summary using means and standard deviations stratified by dosage group for the treatment subgroup during the blinded study phase will be performed. The partial eta squared effect size difference will be estimated.

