Reference Therapy	The investigational product will be compared to placebo, a nasal spray consisting of magnesium, chloride crystals, citric acid anhydrous gran., sodium citrate powder, sterile water for irrigation, and Pcca Mucolox liquid base.
Key Procedures	Oxytocin (or placebo) will be self – administered by the study participants daily. Study visits will occur every two weeks, from prior to the baseline week to 15 weeks after baseline, during which patients will be asked to rate the loudness of their tinnitus (VAS scale) and complete the THI questionnaire. Additional questionnaires and urinalysis will be performed at every study visit to monitor sodium levels and osmolality.
Statistical Analysis	The primary analysis is to provide an estimate of the partial eta squared effect size difference between placebo and treatment during the blinded phase of the study as well as to provide initial efficacy, safety and tolerability estimates during the initial open label study phase.

Schematic of Study Design

1 Key Roles

Primary investigator: [name] NYU Langone Medical Center [name] [name] [contact]

Sub-investigator (Headache Fellow): [name], MDNYU Langone Medical Center [name] [name] [contact]

Research Coordinator, Regulatory Specialist, Data Management, and Primary Contact: [name] NYU Langone Medical Center [name] [name] [contact]

2 Introduction, Background Information and Scientific Rationale

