2.4.1.2 Known Potential Benefits

Subjects may or may not directly benefit from being in the study. Close medical monitoring of their symptoms may be a potential benefit if subjects are seen infrequently otherwise. Furthermore, if the medication is effective for tinnitus, participants may indeed improve. However, the overall benefit of participating in this research is that it may help others with tinnitus in the future.

3 Objectives and Purpose

The purpose of this study is to evaluate the effects of high-dose intranasal oxytocin for treating tinnitus.

The primary outcome measurement will be a change in the VAS at 3 timepoints:

1. Comparative endpoint of VAS of all 30 subjects at 9th week of treatment with active drug vs baseline.

2. Comparative endpoint during the cross-over phase of VAS at the 17th visit (15th week of study) between the 15 subjects who received placebo vs the 9th week of the non-blinded phase for the same subjects (when they were on active drug). This endpoint compares the 15 patients that were switched from active to placebo and compares their response on placebo (from the double blind phase) with their response on active drug (from the non-blinded phase) and compares them to the 15 subjects that remained on active drug during the entire study.

3. A parallel group analysis where we compare both arms in the last week of the double-blind phase—so in essence we are comparing those 15 who were on active throughout the entire study to those that started on active and changed over to placebo.

Secondary endpoints of interest are also defined a-priori:

1. A change in the THI by at least one grade contrasting the 9th week (end of the single blinded phase) and the 15th week of the study (end of the double blinded phase) between the 15 subjects who were switched from active drug to placebo.

2. A change in the THI by at least one grade during the last 2 weeks of the double-blind stage (weeks 14 and 15 of the study contrasting those on active drug vs. placebo.

Exploratory endpoints of interest include:

Clinical Global Impression (CGI) measured following the same approach of the primary endpoints. Tinnitus Functional Index (TFI) measured following the same approach of the primary endpoints.

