4.2 Study Endpoints

4.2.1.1 Primary Study Endpoints

The primary outcome measurement will be the collective area under the Visual Analog Scale (VAS) curve above the week 3 baseline as assessed from week 3 to week 6 of the double blinded study phase.

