7.2.3 Intermediate Visits

7.2.3.1 Visit 3: End of Week 1 (Office Visit)

- Record adverse events as reported by participant or observed by investigator.
- Record vital signs and auscultate lungs.
- Review current medications and results of VAS log.
- Perform urine pregnancy test, if applicable.
- Administer THI questionnaire.
- Provide the study medication to the participant to use four times daily for the next 2 weeks.

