7.2.3.2 Visit 4: Week 2 (Phone Visit)

- Review current medications.
- Assess and record adverse events including dyspnea as reported by participant or observed by investigator.
- Record participant's adherence to treatment program.
- Administer phone Tinnitus Functional Index (TFI) questionnaire.

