7.2.3.9 Visit 11: Week 9 (Office Visit)

- Record vital signs and auscultate lungs.
- Review current medications and results of VAS log.
- Collect urine for electrolyte levels and urine osmolality. Perform urine pregnancy test, if applicable.
- Administer THI and CGI-I questionnaires.
- Record adverse events as reported by participant or observed by investigator.
- Study drug reconciliation and record of participant's adherence to treatment program.
- Randomize and dispense new study drug (active drug or placebo nasal spray) to use for the next 2 weeks.

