7.2.5 Withdrawal/Early Termination Visit

If the participant agrees, any participant who withdraws from the study or is terminated early, will be asked to come in for a final visit in which we will record vital signs, obtain blood for CMP, record adverse events, and review results of VAS, THI and CGI.

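### The planned TFI change has no listed end value, no analysis section assigns blinded week 3 to a visit, and the THI event is worded in three incompatible ways

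*Combined protocol and SAP*

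**What the plan says.** **Planned changes.** Section 9.4.7.6 (Exploratory Analyses): "Changes in CGI and TFI from baseline (week 3) to week 6 during the blinded study phases will be determined". Section 3 adds "Tinnitus Functional Index (TFI) measured following the same approach of the primary endpoints"; the time points used there are baseline, Week 9 and Week 15.

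**Collection.** Sections 4.1 and 7.1 describe the TFI as completed by telephone. In the itemised lists of Section 7.2, each phone visit from Visit 4 on has "Administer phone Tinnitus Functional Index (TFI) questionnaire". Visit 3, where active drug is first dispensed, has "Administer THI questionnaire". Visit 11, where randomisation takes place, has "Administer THI and CGI-I questionnaires", and Visits 13, 15 and 17 name the same two instruments. The early-termination visit (7.2.5) will "review results of VAS, THI and CGI". In contrast, the tables in 7.1.1 and Section 18 mark questionnaires at every visit without naming them, and the Protocol Summary says "Additional questionnaires and urinalysis will be performed at every study visit to monitor sodium levels and osmolality".

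**Anchor.** Section 4.2.1.1: "The primary outcome measurement will be the collective area under the Visual Analog Scale (VAS) curve above the week 3 baseline". Sections 9.2, 9.4 and 9.4.2 use the same baseline, and the last two place it after a two-week washout. None of them gives a visit number or study week.

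**THI event.** For the change from blinded week 3 to week 6, Sections 4.2.1.2 and 9.2 count changes of more than one grade, Sections 9.4 and 9.4.3 count one point or more, and Section 9.4.1 counts more than one point. Section 3 uses one grade or more, for other windows.

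**The concern.** A change score needs a value at both ends. If the TFI is collected only where the visit lists name it, the planned change to blinded week 6 cannot be calculated. Section 9.4 allows the analyses to be refined before data lock, but that cannot supply a value that was not collected.

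The undefined baseline visit matters more widely, because the same anchor fixes the start and the subtracted value of the primary VAS area. The pilot's stated purpose (9.5) is to estimate an effect size for a later trial, so the anchor should not be left open until the data are visible.

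The THI wordings mix two units and two inequalities, so the same participant can be an event in one section and a non-event in another. The defining sentences give no direction of change, although the Protocol Summary and Section 4.1 speak of improvement.

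**Working it through.** The plan gives no figure of its own to reproduce here. The check sets the schedule against the definitions and then shows by arithmetic what the choices move.

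**1. Visit map.** Randomisation is at Visit 11 (Week 9), and Section 3 makes Week 15 the end of the blinded phase. Blinded week k therefore ends at study week 9 + k.

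| Visit | Study week | Blinded week | Questionnaires named in 7.2 |
|---|---|---|---|
| 11 | 9 | 0 | THI, CGI-I |
| 12 | 10 | 1 | TFI |
| 13 | 11 | 2 | THI, CGI-I |
| 14 | 12 | 3 | TFI |
| 15 | 13 | 4 | THI, CGI-I |
| 16 | 14 | 5 | TFI |
| 17 | 15 | 6 | THI, CGI-I |

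Over all 17 visits the lists name THI at 10, TFI at 7 and CGI-I at 7. No visit names both THI and TFI.

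**2. Values listed for a change from blinded week 3 to week 6.**

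| Reading of week 3 | TFI | THI | CGI-I |
|---|---|---|---|
| Visit 14 (Week 12) | start only, 1 of 2 | end only, 1 of 2 | end only, 1 of 2 |
| Visit 13 (Week 11) | 0 of 2 | 2 of 2 | 2 of 2 |

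Neither reading makes every planned change computable from the lists. For the Section 3 TFI comparisons (baseline, Week 9, Week 15) the count is 0 of 3: all seven TFI visits come after first dispensing, and Visits 11 and 17 do not name it.

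**3. Which visit is week 3?** Counting three weeks from Week 9 gives Week 12, Visit 14. The version 1.7 entry in the version history also links passing the washout to Week 12 (Visit 14), but as a completion target rather than a baseline. A baseline taken when a two-week washout ends fits Week 11, Visit 13.

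**4. Primary VAS area.** The window to Week 15 is 4 weeks from Visit 13 and 3 weeks from Visit 14. For an assumed steady change of 1 point per week, the area above baseline is ½ × (window)²:

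- start at Week 11: ½ × 4² = 8.0 point-weeks
- start at day 15 after randomisation: ½ × (27/7)² = 7.4
- start at Week 12: ½ × 3² = 4.5

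The gap depends on the shape. A change that starts only after Week 12 gives the same area from both starts (4.5 and 4.5 at 1 point per week).

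The planned statistic is partial eta squared, not the raw area. In simulation with 15 per arm, a flat active arm, daily SD 0.5 and between-participant slope SD 0.3 per week (all assumed), the mean eta squared from a Week 11 and a Week 12 start was:

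| Assumed placebo course | Week 11 | Week 12 |
|---|---|---|
| drift of 0.5 point per week | 0.31 | 0.26 |
| 3-point relapse, 2-week half-time | 0.19 | 0.11 |
| 3-point relapse, 1-week half-time | 0.12 | 0.06 |

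**5. THI event.** A change of exactly one grade is not an event under 4.2.1.2 and 9.2. A change of exactly one point is an event under 9.4 and 9.4.3 but not under 9.4.1. A change of two or more points within a grade is an event only under the point wordings. As an illustration, assume no true mean change, a change SD of 5 to 15 points and equal grade widths of 16 to 24 points. The share counted is then 91–97% (one point or more), 76–91% (more than one point) and 0–10% (more than one grade); Section 3's one grade or more would give 18–60%. With 15 per arm, each reclassified participant moves an arm's percentage by 1/15 = 6.7 points.

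**The case against.** **The TFI may be collected at every visit.** The schedule tables mark questionnaires throughout, and the lists are incomplete elsewhere. Sections 4.1 and 7.1 have VAS administered at office visits, but the office lists show only log review. The lists for Visits 13 and 15 omit the drug reconciliation shown in 7.1.1. Absence from a list is therefore weak proof. A reader might infer that the TFI end value is never collected; the documents show only that it is not listed. The specific text does run one way, though: every TFI entry, and the prose in 4.1 and 7.1, is for the phone.

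**THI may also be weekly.** Section 8.6 screens for depression and suicidality at weekly follow-up visits partly through the THI, which could put a THI at Visit 14. This stands as a further passage to reconcile. It does not help the CGI-I or the TFI.

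**Week 3 does point somewhere.** The week count and the version 1.7 entry both favour Visit 14, so it would be too strong to say that nothing ties week 3 to a visit. What stands is that no endpoint or analysis section names the visit or day, and that the washout wording also fits Visit 13.

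**The area example overstates the effect.** With noise-free straight lines, every participant's area shrinks by the same factor (4.5/8.0 = 0.56), which leaves eta squared unchanged. This is correct: any movement depends on curvature and noise, hence on assumed inputs.

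**These are minor endpoints.** Section 4.1 calls the secondary metrics exploratory and says no specific changes are sought. This limits the severity, but later sections still define and count a THI event, and the anchor also governs the primary endpoint. The carry-forward rule in 9.4 and 9.4.2 is written for the VAS area; applied to the TFI, it would impute the end value for everyone.

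**Conclusion.** The point holds and should be fixed; it does not invalidate the trial.

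- **TFI:** on the itemised lists, the change in 9.4.7.6 has one of two values or none, and the Section 3 comparisons have none of three. This assumes that the unnamed questionnaire marks do not include the TFI.
- **Baseline:** blinded week 3 could be Visit 13 or Visit 14, and neither supports all the planned changes from the lists. A reader might infer that the primary endpoint cannot be calculated. It can, because severity is logged daily (6.1.10, 6.2). Its window is 3 or 4 weeks, and its value and eta squared may differ by an amount that the documents do not determine.
- **THI:** the week 3 to week 6 event has three incompatible wordings. A reader might count four by adding Section 3, but its one-grade criterion applies to Week 9 against Week 15 and to the last two blinded weeks. It is a separate inconsistency of threshold.
- **CGI (minor):** the follow-up lists name the CGI-I, an improvement rating, so a change in CGI is not defined by the data listed.

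**What to change.** Before unblinding:

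1. Name one blinded baseline visit, and the exact daily-log value used for VAS, for all blinded-phase endpoints, with Visit 17 as the end.
2. List the TFI at Visit 17, and at the baseline visit if it is not already there. Add a pre-dose visit and Visit 11 only if the Section 3 TFI comparisons are kept. Alternatively, restate the TFI window as Visit 14 to Visit 16.
3. Use one THI definition in grades, stating threshold, grade boundaries and direction. Delete the point wordings in 9.4, 9.4.1 and 9.4.3.
4. If Visit 14 is the baseline, collect THI and CGI-I there, and reconcile this with Section 8.6.
5. Summarise the Visit 17 CGI-I rating by arm in place of a change in CGI.
6. Name the instruments for each visit in the 7.1.1 table and in Section 18.

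**Cost.** No new visits. The change in 9.4.7.6 needs one extra TFI (baseline at Visit 14) or two (Visit 13). Keeping the Section 3 comparisons brings this to three or four, so 10 or 11 TFI administrations instead of 7. Office TFIs would differ in mode from the phone TFIs, and this should be noted. The alternative window adds no burden but spans only two weeks and ends one week early. A Visit 14 baseline adds one THI and one CGI-I by phone. The amendment needs IRB approval (12.2).

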7.2 Study Schedule

7.2.1 Screening

Screening Visit

- Obtain informed consent of potential participant verified by signature on written informed consent for screening form.
- Review medical history to determine eligibility based on inclusion/exclusion criteria.
- Review medication history to determine eligibility based on inclusion/exclusion criteria.
- Obtain demographic information, alcohol and tobacco use history.
- Perform medical examinations and ECG needed to determine eligibility based on inclusion/exclusion criteria.
- Draw blood for CMP to determine eligibility.
- Collect urine for electrolyte levels, urine osmolality, and pregnancy test if applicable.
- Perform questionnaires including the Tinnitus Handicap Inventory (THI), Clinical Global Impression (CGI) for baseline, and suicidality history.
 - Due to the correlation between tinnitus and suicide, the investigator will evaluate suicidality history by patient interview to be recorded in the CRF. This will be re-assessed at follow up visits as a part of the THI. If a subject reports suicidal ideation or intent at any time, they will immediately be referred to a psychiatrist or psychiatric emergency department.
- Schedule study visits for participants who are eligible and available for the duration of the study.

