7.2.2 Enrollment/Baseline

Visit 2: Baseline Visit – Beginning of Week 1 (Phone Visit)

- Review of current medications.
- Administer THI and VAS questionnaires.
- Issue daily Tinnitus Severity Log/Visual Analog Scale (VAS) log by email.

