7.2.3.3 Visit 5: Week 3 (Office Visit)

- Record vital signs and auscultate lungs.
- Review current medications and results of VAS log.
- Collect urine for electrolyte levels and urine osmolality. Perform urine pregnancy test, if applicable.
- Administer THI and Clinical Global Impression Improvement (CGI-I) questionnaires.
- Record adverse events as reported by participant or observed by investigator.
- Study drug reconciliation and record of participant's adherence to treatment program.
- Provide the study medication to the participant to use four times daily for the next 2 weeks.

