7.2.4 Final Study Visit

Visit 17: Week 15 (Office Visit)

- Record vital signs and auscultate lungs.
- Review current medications and results of VAS log.
- Draw blood for CMP to be able to compare to baseline levels.
- Perform urine pregnancy test, if applicable.
- Administer THI and CGI-I questionnaires.
- Record adverse events as reported by participant or observed by investigator.
- Study drug reconciliation and record of participant's adherence to treatment program.

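### The planned blinded-phase CGI change differences two improvement ratings, and no CGI is scheduled at its week 3 baseline

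*Combined protocol and SAP*

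**What the plan says.** Two places plan a CGI analysis. Section 9.4.7.6 reads "Changes in CGI and TFI from baseline (week 3) to week 6 during the blinded study phases will be determined" and summarises the result by mean and standard deviation in each arm. Section 3 lists among the exploratory endpoints "Clinical Global Impression (CGI) measured following the same approach of the primary endpoints". The first of those primary contrasts is Week 9 against baseline, and another sets Week 15 against Week 9.

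The visit lists in Section 7.2 show what is collected:

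- Screening (7.2.1): "Clinical Global Impression (CGI) for baseline", with no version of the scale named.
- Visit 2 (7.2.2): "Administer THI and VAS questionnaires". No CGI.
- Visit 3, before the first dose (7.2.3.1): "Administer THI questionnaire". No CGI.
- Visit 5, Week 3 (7.2.3.3): "Administer THI and Clinical Global Impression Improvement (CGI-I) questionnaires". Visits 7 and 9 have the same entry.
- Visits 11, 13, 15 and 17 (Weeks 9, 11, 13 and 15): "Administer THI and CGI-I questionnaires".
- Phone visits from Week 2 to Week 14: the TFI, and no CGI.

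Sections 4.1, 7.1 and 7.2.5 mention the CGI without a version, and the Section 18 schedule has a single row for all questionnaires. None of these adds a later status rating, and no section gives the time point against which CGI-I is rated.

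**The concern.** A change score needs the same status measure at two times. Here the measure collected after screening is itself a judgement of change. Subtracting one such rating from another has a clear meaning only if both refer to the same fixed time, and the plan does not fix one. The subtraction also needs a rating at the named starting week, and none is scheduled there.

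At stake is how readable one exploratory outcome will be. Section 4.1 groups the CGI with the THI and TFI as results meant to guide the next, larger study. If raters use different reference points, or the analyst has to choose a substitute baseline visit after the fact, the CGI summary by arm cannot serve that purpose.

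**Working it through.** The plan states no figure that rests on the CGI, so there is none to reproduce. The check sets the visit lists against the two planned analyses, then tests on an assumed scale when a subtraction misleads.

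**1. Is the baseline rating collected?** Randomisation is at Visit 11 (Week 9), so blinded week k is study week 9 + k. Blinded week 3 is Week 12 (Visit 14) and blinded week 6 is Week 15 (Visit 17). Visit 14 is a phone visit with the TFI only; Visit 17 has CGI-I. The starting value is missing by design. The nearest CGI-I ratings are at Weeks 11 and 13. The version 1.7 entry in the version log agrees with this mapping, since it ties passing the washout to data through Week 12, Visit 14. The TFI has the mirror-image gap: it is listed at Visit 14 but not at Visit 17.

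**2. Scale assumption.** The documents give no scale points. For illustration, assume 7-point scales: status from 1 (not ill) to 7 (most ill), and CGI-I with 1 = very much improved, 4 = no change and 7 = very much worse. Negative differences then read as improvement.

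**3. Week 9 against baseline, if done by subtraction (Section 3).** Let S be the screening status and I the Week 9 CGI-I; the computed change is I − S. For a participant rated no change (I = 4):

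| S | 2 | 3 | 4 | 5 | 6 | 7 |
|---|---|---|---|---|---|---|
| 4 − S | +2 | +1 | 0 | −1 | −2 | −3 |

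Across all 7 × 7 = 49 pairs, compare the sign of I − S with the direction that CGI-I itself reports, the sign of I − 4. Disagreements number 6 at I = 4, plus 1, 2 and 3 at I = 1, 2 and 3, and the same at I = 7, 6 and 5: 6 + 2 × (1 + 2 + 3) = 18 of 49. Full reversals number 2 × (0 + 1 + 2) = 6; for example, S = 6 and I = 5 (minimally worse) gives 5 − 6 = −1. With S limited to 3–6, there are 7 disagreements in 28 pairs, 1 of them a reversal. This problem does not depend on the CGI-I reference point.

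**4. Difference of two CGI-I ratings (Section 9.4.7.6).** Let a be the earlier and b the later rating at consecutive office visits such as Weeks 13 and 15; the computed change is b − a.

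- Both rated against one fixed pre-treatment state: the sign of b − a is right for every pair.
- Each rated against the previous visit: the change between the two visits is b − 4, not b − a. The count is as in step 3: 18 of 49 pairs disagree and 6 are reversed. For example, a = 2 then b = 3 is improvement reported at both visits, but b − a = +1 reads as worsening.

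These counts show what is possible, not how often it would happen.

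**The case against.** The strongest reply is that the CGI is exploratory. Section 4.1 says so and disclaims any search for specific changes, Section 9.4.7.6 is descriptive, and no success rule uses the CGI. That stands, and it limits the severity.

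A second reply is that Section 3 does not prescribe subtraction. A Week 9 CGI-I rated against the pre-treatment state already is the comparison of Week 9 with baseline, and Section 9 specifies no open-label CGI analysis. This also stands: the mixing of scales is conditional on how Section 3 is carried out. That the screening item is a status score is likewise inferred, from its being taken before any treatment.

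Third, week 3 might be read as the visit that closes the two-week washout, Visit 13 (Week 11), where CGI-I is collected. The plan does not say this. Section 9.4 treats the first two blinded weeks as washout, and the version log points to Week 12. Even on this reading, two change ratings would be differenced.

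Stronger conclusions are tempting but not supported:

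- A reader might infer that the blinded CGI change will score a placebo relapse as improvement: CGI-I of 6 at Week 11, then 4 at Week 15, gives 4 − 6 = −2. That requires rating against the previous visit, which no section states; the screening label "Clinical Global Impression (CGI) for baseline" leans towards a fixed reference. It also starts from Week 11, inside the washout. From Week 13 the same participant, stable since Week 11, scores 4 − 4 = 0.
- A reader might object that participants rated very much improved throughout and unchanged throughout both score 0. Any change score does that to stable participants, including the VAS area measured from week 3. It is not a fault of CGI-I.

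**Conclusion.** The point holds as a minor one. Two parts need no assumption about scale points: Section 9.4.7.6 plans a change in a measure that is, from the first on-treatment office visit, recorded only as a change rating with no stated reference; and no CGI is scheduled at the blinded week 3 named as its baseline, so the figure cannot be computed as written.

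Two further parts are conditional. The Week 9 contrast mixes two kinds of score only if Section 3 is carried out as a subtraction and the screening item is a status rating. The blinded difference has the wrong sign only if CGI-I is rated against the previous visit. The 18 of 49 disagreements in each case rest on the assumed 7-point coding.

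It would be wrong to infer that the main result is at risk. The primary VAS endpoint and the sample size of 30 do not depend on the CGI.

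**What to change.** - State on the CGI-I form and in the SAP one fixed reference for all visits: the participant's state before treatment.
- Do not subtract CGI-I. In Section 9.4.7.6 and in the CGI line of Section 3, replace the change with CGI-I as rated: Week 9 overall, and Week 15 by arm, as a distribution or as improved / no change / worse, with the Week 9 rating by arm alongside.
- If a change score is wanted, repeat the screening CGI item at the existing office visits used in the contrast and take changes on that item only.
- While editing Section 9.4.7.6, match the named weeks to visits where each scale is given; the TFI needs this too.

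The cost is a sentence on the form and a few lines of SAP text, with no new visits. There are two downsides. A Week 15 rating against the pre-treatment state also carries the open-label response, which is why Week 9 by arm should be shown beside it. Ratings already made without a stated reference cannot be redone, so the report should say which ratings predate the change.
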